### I. Comparison between patients in group I and group II regarding age.

The age in group I ranged from 16-42 years with mean value  $26.12\pm6.34$  and in group II ranged from 15-41 years with mean value  $24.66\pm5.59$ . There was no statistically significant difference between the two studied groups regarding age (P= 0.067) (Table 1, Fig. 14)

Table (1): Comparison between the two studied groups regarding age.

	Group I	Group II			
Age (years)					
Range	16-42	15-41			
Mean	26.12	24.66			
SD	6.34 5.59				
T test	1.68				
P value	0.067				

Group I. cesarean section with bladder dissection Group II: cesarean section without bladder dissection t-test = student t-test p was significant if  $\leq 0.05$ 

[figure not shown]

Figure (14): Comparison between the two studied groups regarding age.

### II-Comparison between two groups as regard obstetric history

Gravidity in group I had mean value  $1.44\pm1.03$  and in group II had mean value  $1.312\pm0.737$ . Parity in group I had mean value  $0.136\pm0.68$  and in group II had mean value  $0.192\pm0.73$ . It was found that most of cases had no abortion in two studied groups 97(77.6%) and 99(79.2%) respectively. No ectopic cases was higher with 125(100%) and 124(99.2%) respectively. Gestational age had mean value  $37.41\pm2.37$  and in group II had mean value  $36.99\pm2.50$ .

[figure not shown]
There were no statistically significant differences between the two studied groups regarding gravidity (P = 0.133), parity (P = 0.069), abortion (P=0.465), ectopic (P=0.159) and gestational age (P = 0.175). (Table 2, Fig. 15)

[figure not shown]
Obstetric history	Group I	Group II	T test P value
Gravidity			
Range	1-9	1-6	0.133
Mean	1.44	1.312	0.155
SD	1.03	0.77	
Parity			
Range	0-6	0-4	0.069
Mean	0.142	0.192	0.009
SD	0.68	0.73	
Abortion			
No	97 (77.6%)	99 (79.2%)	0.465
1-2	27 (21.6%)	23 (18.4%)	0.403
>2	1 (0.8%)	3 (2.4%)	
Ectopic			
No	125(100.0%)	124 (99.2%)	0.159
Yes	0.0 (0.0%)	1 (0.8%)	
Gestational age			0.175

[figure not shown]
Table (2): Comparison between the two studied groups regarding obstetric history.

Range	34-41	33-41	
Mean	37.41	36.99	
SD	2.37	2.50	

Group I. cesarean section with bladder dissectiont-test = student t-testGroup II: cesarean section without bladder dissection p was significant if  $\leq 0.05$ 

[figure not shown]

Figure (15): Comparison between the two studied groups regarding obstetric history.

[figure not shown]
#### III-Comparison between two groups as regard uterine position

AVF position in both groups was higher 108(86.4%) and 116(92.8%) respectively followed by RVF position with 15(12%) and 8(6.4%) respectively, erect position was equal in both groups with 1(0.8%). There was statistical significant increase in group I than group II regarding the RVF position (P=0.03). (Table 3, Fig. 16)

Table (3): Comparison between the two studied groups regarding the uterus position.

Uterus	Group I		Gro	up II	P value
position	No	%	No	%	
AVF	109	87.2	116	92.8	0.265
RVF	15	12.0	8	6.4	0.03*
Erect	1	0.8	1	0.8	1.0

Group I. cesarean section with bladder dissection Group II: cesarean section without bladder dissection  $X^2$  = Chi square-test p was significant if  $\leq 0.05$ \* = Significant at level 0.05

**Figure (16):** Comparison between the two studied groups regarding the uterus position.

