#### 5. Retroflexed Uterus

Effect of gravity on uterine corpus also increases counteracting forces. Large niches are mostly found with retroflexed uterus. 

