# RESULTS

This study was prospectively conducted on 250 women recruited from ElShatby university maternity hospital delivery ward; they were randomized into two groups group (A) and group (B) by closed envelop randomization.

Group (A) was undergo cesarean section with bladder dissection.

Group (B) was undergo cesarean section without bladder dissection.

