## IV-Comparison between two groups as regard incidence of niche

Niche is defined as an anechoic space at least 2 mm depth at the presumed site of the caesarean section scar.

The incidence of niche was higher in group I, yet it did not reach statistical significance. (P=0.087). (Table 4, Fig. 17)

Table (4): Comparison between the two studied groups regarding incidence of niche

Incidence of niche	Group I		Group II		
	No %		No	%	
Absent	89	71.2	99	79.2	
Present	35	28.0	26	20.8	
X 	1.94				
P value	0.087				

Group I. cesarean section with bladder dissection Group II: cesarean section without bladder dissection  $X^2$  = Chi square-test p was significant if  $\leq 0.05$ 

[figure not shown]

Figure (17): Comparison between the two studied groups regarding incidence of niche

[figure not shown]

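### Table 3 calls the RVF excess in group I significant at P=0.03, but the printed counts (15 v 8 of 125) give P=0.126

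*SAP*

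**What the plan says.** The SAP document (Results, section III) compares uterine position between group I (bladder dissection) and group II (no dissection). The text gives the counts: "AVF position in both groups was higher 108(86.4%) and 116(92.8%) respectively followed by RVF position with 15(12%) and 8(6.4%) respectively". It then concludes: "There was statistical significant increase in group I than group II regarding the RVF position (P=0.03".

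Table 3 prints three rows:

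| Position | Group I | Group II | Printed P |
|---|---|---|---|
| AVF | 109 (87.2%) | 116 (92.8%) | 0.265 |
| RVF | 15 (12.0%) | 8 (6.4%) | 0.03* |
| Erect | 1 (0.8%) | 1 (0.8%) | 1.0 |

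The footnote identifies the test and threshold ("Chi square-test p was significant if" at or below 0.05) and explains the asterisk as significance at that level. It does not say whether tests are one- or two-sided. The AVF count for group I is 108 in the text and 109 in the table.

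**The concern.** Fifteen cases against eight, in groups of 125, is too small a difference to give P=0.03 with a chi-square test. The counts, the percentages and the P value each appear in both text and table and agree there, so the mismatch is not a broken table.

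RVF is the only row marked significant in Tables 1 to 3. The abbreviation is not expanded. If it denotes a retroverted or retroflexed uterus (an assumption), the protocol's introduction ties that position to the outcome: "Large niches are mostly found with retroflexed uterus". A reader would then carry a supposedly established difference in a niche-related factor into Table 4 (niche in 28.0% v 20.8%) and Table 5 (niche length and width reported as significantly larger in group I). It could be read as confounding or as an effect of bladder dissection. The printed counts establish neither.

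**Working it through.** **Inputs.** RVF 15 v 8 (section III text and Table 3). The denominator is 125 per group: 15/125 = 12.0% and 8/125 = 6.4% match the printed percentages, and the Table 3 columns sum to 109+15+1 = 125 and 116+8+1 = 125. The 2x2 table is therefore 15/110 v 8/117.

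**Attempt to reproduce P=0.03 with the named test.** Pearson chi-square = N(ad - bc)² / (product of the four margins)

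= 250 × (15×117 - 110×8)² / (125 × 125 × 23 × 227)

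= 250 × 875² / 81,578,125 = 2.346, 1 df, P=0.126.

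P=0.03 needs a chi-square of about 4.71. The printed figure is not reproduced.

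**Other tests and denominators.**

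| Test on RVF | Two-sided P | One-sided P |
|---|---|---|
| Pearson, 15/125 v 8/125 | 0.126 | 0.063 |
| Continuity-corrected | 0.189 | 0.095 |
| Fisher exact | 0.188 | 0.094 |
| Unpooled z | 0.124 | 0.062 |
| Pearson, 15/124 v 8/125 | 0.121 | 0.060 |
| RVF v AVF only (AVF 109 or 108 in group I) | 0.125 or 0.120 | - |

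Likelihood-ratio (0.123), Barnard and Boschloo (both 0.131) and a t-test on 0/1 data (0.127) agree. None is below 0.05.

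**Size of the difference.** 12.0% - 6.4% = 5.6 points. The Wilson limits are 7.4% to 18.9% and 3.3% to 12.1%. Newcombe's method combines them: lower limit 5.6 - √[(12.0-7.4)² + (12.1-6.4)²] = -1.7, upper limit 5.6 + √[(18.9-12.0)² + (6.4-3.3)²] = 13.1 (computed from unrounded limits). Odds ratio = (15×117)/(110×8) = 1.99. The standard error of its log is √(1/15 + 1/110 + 1/8 + 1/117) = 0.457, giving 95% CI 0.81 to 4.89.

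**Can the 108 v 109 conflict explain it?** With 108, group I sums to 108+15+1 = 124, so one woman is unplaced. Leaving her out gives P=0.121. Counting her as RVF (16 v 8) gives P=0.086, Fisher 0.13. Neither is 0.03.

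**What would give it, two-sided Pearson?** With 8 in group II, 18 in group I gives 0.038 and 19 gives 0.025. With 15 in group I, 6 in group II gives 0.040 and 5 gives 0.020. Reaching 0.03 or below therefore needs a count to be wrong by 3 or 4 women.

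**The AVF row.** 109/125 v 116/125: 250 × (109×9 - 16×116)² / (125 × 125 × 225 × 25) = 2.178, P=0.140, Fisher 0.205. The printed 0.265 is not reproduced either. Using 108 gives 0.097 (of 125) or 0.134 (of 124), which are further away.

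**All three positions at once.** The exact (Fisher-Freeman-Halton) test gives P=0.28 with 109 and 0.26 with 108.

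**The case against.** The strongest counter-argument is that the tests may be one-sided, since the documents do not say. Some other printed values fit that reading. In Table 4, 35/124 v 26/125 gives a one-sided P of 0.087, the printed value (two-sided 0.173). In Table 2, ectopic pregnancy, 0 v 1 of 125, gives 0.158 one-sided against a printed 0.159 (two-sided 0.316). Niche length, taking n=35 and 26, gives 0.010 one-sided, as printed (two-sided 0.020). The pattern is not uniform: gestational age (0.175) fits a two-sided test. On a one-sided reading, 16 v 8 gives 0.043 and 17 v 8 gives 0.029, so the discrepancy could be two women rather than three or four.

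This stands as a caution. The figure of 3 or 4 women holds only for a two-sided test, and one misplaced woman plus a one-sided test would fall below 0.05. It does not rescue the printed result: one-sided Pearson on 15 v 8 is 0.063, and even 16 v 8 does not give 0.03.

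Two limits on relevance also stand. Uterine position is not among the protocol's four outcome measures, and no analysis shown adjusts for it. The documents do not say when position was recorded. The only examinations of the uterus that the protocol describes are the scans at 3 and 6 months, so it may be a postoperative finding rather than a baseline factor.

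**Conclusion.** The concern holds. P=0.03, the asterisk and the sentence claiming a significant increase do not follow from 15 v 8 of 125. The named test gives P=0.126, which reverses the conclusion at the document's own 0.05 level. This rests only on the printed counts and a denominator of 125; using 124 or a one-sided test does not change it.

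The documents cannot show whether the P value or a count is the misprint. Nor does P=0.126 show that the groups were alike, since the odds ratio interval runs from 0.81 to 4.89. The niche result itself is unaffected. The harm is a false significance statement about a factor that, if RVF means what it appears to, the protocol links to large niches.

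**What to change.** 1. Check the uterine-position counts against source data. Reconcile 108 with 109, and state whether 124 or 125 women in group I had a position recorded. Table 4 has the same one-woman shortfall in group I (89+35 = 124), so the two can be checked together.
2. Expand the abbreviations, say when position was recorded, and state whether the P values are one- or two-sided, using the same convention in every table.
3. Recompute Table 3. If the table's counts stand and tests are two-sided, print RVF P=0.13 (Fisher 0.19) and AVF P=0.14 (Fisher 0.21). A single exact test across the three positions (P=0.28) is an alternative, because the Erect row has an expected count of 1 per group, too sparse for chi-square.
4. Remove the asterisk. Replace the sentence on RVF with the observed 12.0% v 6.4%, difference 5.6 points (95% CI -1.7 to 13.1), described as not statistically significant and without a claim of balance. If a count changes, restate the comparison from the corrected count.

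The cost is a source check of one variable, one table re-run and one sentence reworded, plus a line on sidedness. If that line shows mixed conventions, the affected P values in other tables need re-running too. No new data are needed.

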## IV-Comparison between two groups as regard incidence of niche

Niche is defined as an anechoic space at least 2 mm depth at the presumed site of the caesarean section scar.

The incidence of niche was higher in group I, yet it did not reach statistical significance. (P=0.087). (Table 4, Fig. 17)

Table (4): Comparison between the two studied groups regarding incidence of niche

Incidence of niche	Group I		Group II		
	No %		No	%	
Absent	89	71.2	99	79.2	
Present	35	28.0	26	20.8	
X 	1.94				
P value	0.087				

Group I. cesarean section with bladder dissection Group II: cesarean section without bladder dissection  $X^2$  = Chi square-test p was significant if  $\leq 0.05$ 

[figure not shown]

Figure (17): Comparison between the two studied groups regarding incidence of niche

[figure not shown]

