# **RESULTS**

The results will be tabulated and statistically analyzed, using the standard statistical methods.

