#### V- Comparison between the two groups regarding niche characteristics

[figure not shown]
Length in group I ranged from 0.3-1.1 with mean value  $0.707\pm0.23$  and in group II ranged from 0.32-1.4 with mean value  $0.570\pm0.21$ . Width in group I ranged from 0.35-1.3 with mean value  $0.737\pm0.26$  and in group II ranged from 0.4-1.12 with mean value  $0.640\pm0.19$ . There was statistical significant increase in group I than group II regarding length and width (P=0.010, 0.046). There were no statistical significant differences between the two studied groups regarding depth, AMT and RMT (P= 0.421, 0.441, 0.378). (Table 5, Fig. 18)

Table (5): Comparison between the two studied groups regarding niche characteristics.

Niche characteristics	Group I	Group II	T test P value
Length (cm)			
Range	0.3-1.1	0.32-1.4	0.010+
Mean	0.707	0.570	0.010*
SD	0.23	0.21	
Width (cm)			
Range	0.35-1.3	0.4-1.12	0.046*
Mean	0.737	0.640	0.040*
SD	0.26	0.19	
Depth (cm)			
Range	0.21-0.80	0.20-0.49	0.421
Mean	0.331	0.317	0.421
SD	0.15	0.09	
AMT			
Range	0.85-1.6	0.92-1.39	0.441
Mean	1.109	1.115	0.441
SD	0.16	0.14	
RMT			
Range	0.24-1.4	0.34-0.92	0.378
Mean	0.716	0.701	0.376
SD	0.21	0.15	

Group I. cesarean section with bladder dissection Group II: cesarean section without bladder dissection t-test = student t-test p was significant if  $\leq 0.05$  \* = Significant at level 0.05

[figure not shown]

Figure (18): Comparison between the two studied groups regarding niche characteristics.

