# VI- Comparison between the two groups regarding post delivery complain

[figure not shown]
The incidence of post-delivery complaint (HMB, Intermenstrual spotting and post coital bleeding) after 6 months was more in group I than group II, but it did not reach statistical significance. The most common complaint was spotting 8(61.5%) v.s 4(50%) followed by post coital bleeding 3(23.1%) v.s 2(25%).

So ,There was no statistical significant difference between two studied groups regarding post-delivery complain (P= 0.621, 0.102)

Post delivery complain	Gro	Group I		up II	P value
	No	%	No	%	
No	112	89.6	117	93.6	0.621
Yes	13	10.4	8	6.4	0.102
Spotting	8	61.5	4	50.0	0.071
НМВ	2	15.4	2	25.0	1.0
Post coital bleeding	3	23.1	2	25.0	0.92

Table (6): Post delivery complain in the two studied groups.

Group I. cesarean section with bladder dissection Group II: cesarean section without bladder dissection  $X^2$  = Chi square-test p was significant if  $\leq 0.05$ 

[figure not shown]

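### Table 4 (niche incidence): group I counts add to 124 while the percentages use 125, and the printed chi-square of 1.94 and P of 0.087 agree neither with each other nor with a two-sided test of the counts

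*SAP*

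**What the plan says.** The protocol's aim is to compare the incidence of caesarean scar defect with and without bladder flap dissection, and niche incidence comes first under Outcome measures. On analysis, the protocol's Results section says only: "The results will be tabulated and statistically analyzed, using the standard statistical methods". Neither document says whether tests are one- or two-sided.

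The SAP file is written as a results chapter. Section IV states: "The incidence of niche was higher in group I, yet it did not reach statistical significance. (P=0.087". Table 4 gives:

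| | Group I | Group II |
|---|---|---|
| Absent | 89 (71.2%) | 99 (79.2%) |
| Present | 35 (28.0%) | 26 (20.8%) |

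Below these it prints a chi-square of 1.94 and P = 0.087. The footnote names the chi-square test and a 0.05 threshold. The study has 250 women, and Table 2 uses 125 per group.

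**The concern.** Three printed items should follow from one another: the counts, the test statistic and the P value. Here they do not. The group I column is one woman short of the denominator behind its own percentages. The statistic and the P value cannot both be right for a two-sided test on 1 degree of freedom.

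The outcome is the one the study was set up to compare. A P of 0.087 invites the reader to see a near miss. A reader, or anyone pooling this trial with others, also cannot tell whether group I is 35/124, 35/125 or 36/125.

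**Working it through.** **1. Counts and percentages (Table 4).**
- Group I: 89 + 35 = 124. But 89/125 = 71.2% and 35/125 = 28.0%, which add to 99.2%. On 124 they would be 71.8% and 28.2%.
- Group II: 99 + 26 = 125, and 79.2% + 20.8% = 100%. This column is consistent.
- Completing group I to 125 needs either 36 present (28.8%) or 90 absent (72.0%).

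**2. The printed pair against itself.** On 1 degree of freedom, a chi-square of 1.94 gives two-sided P = 0.164. A two-sided P of 0.087 needs a chi-square of 2.93. This check uses only the two printed numbers, so no choice of denominator can repair it.

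**3. The printed pair against the counts.** Uncorrected Pearson chi-square = N(ad − bc)² / (product of the four margins), with group II at 99/26:
- 89/35: 249 × 1151² / (124 × 125 × 188 × 61) = 1.86
- 89/36: 250 × 1250² / (125 × 125 × 188 × 62) = 2.14
- 90/35: 250 × 1125² / (125 × 125 × 189 × 61) = 1.76

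| Group I niche | Pearson statistic | Pearson P | Yates P | Fisher P |
|---|---|---|---|---|
| 35/124 (28.2%) | 1.86 | 0.173 | 0.224 | 0.187 |
| 36/125 (28.8%) | 2.14 | 0.143 | 0.187 | 0.187 |
| 35/125 (28.0%) | 1.76 | 0.185 | 0.239 | 0.239 |

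The Yates statistics (1.48, 1.74, 1.39) and the likelihood-ratio statistics (1.86, 2.15, 1.76) do not give 1.94 either. No two-sided P in the table is 0.087.

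**4. Could the P values be one-sided?** Half the Pearson P for 35/124 v 26/125 is 0.0866, which rounds to the printed 0.087. Half the P for the printed 1.94 is 0.082, so halving does not reconcile the printed pair. I tested the same idea on other printed P values. The method was a pooled t-test from the printed means and SDs (125 per group, or 35 and 26 for niche measurements), and uncorrected Pearson for counts.

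| Comparison | Two-sided | Half | Printed | Fits |
|---|---|---|---|---|
| Gravidity, SD 0.77 as in Table 2 | 0.267 | 0.133 | 0.133 | half |
| Ectopic, as a 0/1 t-test | 0.318 | 0.159 | 0.159 | half |
| Niche length | 0.020 | 0.010 | 0.010 | half |
| AMT | 0.879 | 0.440 | 0.441 | near half |
| RMT | 0.758 | 0.379 | 0.378 | near half |
| Gestational age | 0.174 | 0.087 | 0.175 | full (within 0.001) |
| Age | 0.055 | 0.027 | 0.067 | neither |
| Parity, mean 0.136 | 0.531 | 0.265 | 0.069 | neither |
| Niche width | 0.113 | 0.057 | 0.046 | neither |
| Niche depth | 0.674 | 0.337 | 0.421 | neither |
| RVF position, 15 v 8 | 0.126 | 0.063 | 0.03 | neither |
| Any complaint, 13 v 8 | 0.254 | 0.127 | 0.102 | neither |

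Gravidity fits only with the SD in Table 2; the 0.737 in the text gives 0.260 and 0.130. Parity fits neither value with the Table 2 mean of 0.142 (0.576 and 0.288). The printed values are those in SAP sections I ("There was no statistically significant difference between the two studied groups regarding age (P= 0.067"), II ("gravidity (P = 0.133), parity (P = 0.069), abortion (P=0.465), ectopic (P=0.159) and gestational age (P = 0.175"), III ("There was statistical significant increase in group I than group II regarding the RVF position (P=0.03"), V ("regarding depth, AMT and RMT (P= 0.421, 0.441, 0.378") and VI ("There was no statistical significant difference between two studied groups regarding post-delivery complain (P= 0.621, 0.102"). No single rule explains them all.

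**The case against.** **The inference does not change.** This is right for Table 4. Every two-sided P is between 0.14 and 0.24, the text already calls the difference non-significant, and group I incidence moves by at most 0.8 percentage points. It limits the weight of the point but does not remove it.

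**The halving evidence is mixed and depends on choices.** This also stands. Gestational age contradicts halving. Width is borderline: the table names Student's t-test, but Welch's version gives a half value of 0.049, and rounding in the printed SDs leaves some room around that. The survey leaves out abortion, AVF position and the complaint subtypes. One-sided testing is a possible cause and no more.

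**Rechecking the other tables goes beyond Table 4.** The other discrepancies do not share one demonstrated cause. But two results starred as significant lose that status on a two-sided test of their printed figures: RVF position (0.126, printed 0.03) and niche width (0.113 pooled, 0.098 Welch, printed 0.046). The wider check can therefore change stated conclusions and is worth making.

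**The text may have been misread from the PDF.** Some P values in Tables 2 and 5 appear twice in slightly different form, and 1.94 appears only once. But 0.087 appears in both text and table, and each group I count matches its own percentage on 125. A misread 1.94 would leave the missing woman and the unsupported P value in place.

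**Nothing is labelled primary.** True; the importance of niche incidence is inferred from the aim and from its place at the head of the outcome list.

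**Conclusion.** The concern holds. Table 4 is one woman short in group I. Its chi-square and P value disagree with each other, and neither follows from a two-sided test of the counts. Against the printed 0.087, the two-sided P is 0.14 to 0.19 by uncorrected Pearson and 0.19 to 0.24 by Yates or Fisher. Group I incidence is 28.0%, 28.2% or 28.8% against 20.8% in group II. The non-significant conclusion is unaffected.

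This assumes that the group II column is right and that the gap in group I is one unrecorded woman or one wrong cell. The documents do not show which, and they do not establish where 0.087 came from. The table should be corrected, but the error does not overturn the main finding.

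**What to change.** 1. Query the source data for the 125th woman in group I. If she was not scanned, use 124 as the denominator (28.2% present, 71.8% absent) and say so. If a cell is wrong, correct it to 36 present (28.8%) or 90 absent (72.0%).
2. Re-run Table 4 so that counts, percentages, chi-square and a two-sided P agree, and name any continuity correction.
3. Recompute the P values in the other tables as two-sided, state this in the methods, and revise the text wherever a starred result no longer holds, in particular RVF position and niche width.
4. Separately, reconcile the group I count for AVF position in section III. The text reads "AVF position in both groups was higher 108(86.4%) and 116(92.8%) respectively", but Table 3 shows 109. Table 3 adds to 125 (109 + 15 + 1), while the text figures add to 124 (108 + 15 + 1). This should not be assumed to have the same cause as the gap in Table 4.

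The cost is one data query, one re-run 2×2 table and a recalculation of simple tests. The Table 4 P value moves further from 0.05; the wording on RVF position and width may have to change.

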## PATIENTS

This study will be prospectively conducted on 250 women recruited from ElShatby university maternity hospital delivery ward; They will be randomized into two groups group (A) and group (B) by closed envelop randomization. Group (A) will undergo cesarean section with bladder dissection and group (B) will undergo cesarean section without bladder dissection.

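### Niche incidence and post-delivery complaints are read only by P against 0.05, without a risk difference, risk ratio or confidence interval, so the reader cannot see that both results are inconclusive

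*SAP*

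**What the plan says.** The protocol's aim is to compare the incidence of caesarean scar defect with and without bladder flap dissection, and niche incidence is its first listed outcome. On size it says only: "This study will be prospectively conducted on 250 women recruited from ElShatby university maternity hospital delivery ward". It gives no target difference, power or margin, and its Results section promises only standard statistical methods.

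The document supplied as the SAP is a chapter of tabulated results. Group I had bladder dissection and group II did not. Table 4 (section IV) prints "Absent 89 71.2 99 79.2" and "Present 35 28.0 26 20.8" (count and percentage in group I, then in group II), with X2 = 1.94 and P = 0.087. The text concludes: "The incidence of niche was higher in group I, yet it did not reach statistical significance".

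Section VI says complaints at 6 months were more common in group I but not significantly so, and then concludes: "There was no statistical significant difference between two studied groups regarding post-delivery complain". Table 6 gives 13 (10.4%) against 8 (6.4%) with any complaint. It prints P = 0.621 on the No row and 0.102 on the Yes row.

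The significance rule in the notes to Tables 4 and 6 is P at or below 0.05, with sidedness not stated. No table gives a risk difference, risk ratio, odds ratio or confidence interval.

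**The concern.** Comparing two incidences means estimating how far apart they are and how precisely that is known. A P value set against a threshold gives neither. A result above 0.05 can come from a trial that rules out any sizeable difference or from one that rules out very little, and the text reads the same in both cases. Here neither document states a margin or a sample-size basis, so the reader has nothing else against which to interpret a non-significant result. At stake is whether the main comparison is understood as evidence that the difference is small or as a question still open. The printed P values cannot serve even as a rough guide to precision, because they do not follow from the printed counts.

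**Working it through.** **Inputs.** 250 women were randomised (SAP, Results). Arms of 125 are inferred from "125(100%) and 124(99.2%) respectively" for women with no ectopic pregnancy (SAP section II). Niche: 35 present and 89 absent in group I; 26 present and 99 absent in group II (Table 4). Complaints: 13 and 8 (Table 6).

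**Denominator.** Group I: 35 + 89 = 124, and 28.0% + 71.2% = 99.2%. One woman is missing from the table, although its percentages are calculated on 125. Three readings are possible: 35/124 (she has no result), 35/125 (no niche) and 36/125 (niche). Group II is 26/125 throughout.

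**The printed test.** Pearson chi-square without continuity correction:

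| Group I v 26/125 | X2 | two-sided P |
|---|---|---|
| 35/124 | 1.86 | 0.173 |
| 35/125 | 1.76 | 0.185 |
| 36/125 | 2.14 | 0.143 |

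None gives the printed X2 of 1.94. On 1 df, 1.94 corresponds to P = 0.164, so the printed X2 and P also disagree with each other. The printed 0.087 equals half the Pearson P for 35/124 (0.173/2 = 0.0866).

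For complaints, 13/125 v 8/125 gives X2 = 1.30 and two-sided P = 0.254 (Fisher 0.362). A two-by-two table has one such P, and neither 0.621 nor 0.102 matches it.

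**Interval for the difference (Newcombe).** With d = p1 - p2 and Wilson 95% limits (l1, u1) and (l2, u2) for the two arms:

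lower = d - sqrt[(p1 - l1)² + (u2 - p2)²]

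upper = d + sqrt[(u1 - p1)² + (p2 - l2)²]

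For 35/124 v 26/125: p1 = 0.2823 with Wilson limits 0.2105 and 0.3671; p2 = 0.2080 with limits 0.1461 and 0.2873; d = 0.0743.

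- Lower: 0.0743 - sqrt(0.0718² + 0.0793²) = 0.0743 - 0.1070 = -0.0327
- Upper: 0.0743 + sqrt(0.0848² + 0.0619²) = 0.0743 + 0.1050 = +0.1793

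All readings, group I minus group II, with log-Wald intervals for the risk ratio:

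| Comparison | Risk difference, points (95% CI) | Risk ratio (95% CI) |
|---|---|---|
| Niche 35/124 v 26/125 | +7.4 (-3.3 to +17.9) | 1.36 (0.87 to 2.11) |
| Niche 35/125 v 26/125 | +7.2 (-3.5 to +17.7) | 1.35 (0.86 to 2.10) |
| Niche 36/125 v 26/125 | +8.0 (-2.7 to +18.5) | 1.38 (0.89 to 2.15) |
| Complaint 13/125 v 8/125 | +4.0 (-3.1 to +11.3) | 1.63 (0.70 to 3.78) |

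**What 125 per arm can detect.** Normal approximation with pooled null variance, two-sided 0.05, base p2 = 0.208:

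power = Φ{[d - 1.96·sqrt(2p̄(1 - p̄)/125)] / sqrt([p1(1 - p1) + p2(1 - p2)]/125)}, where p̄ = (p1 + p2)/2.

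For d = 0.16, p1 = 0.368 and p̄ = 0.288: Φ[(0.16 - 0.1123)/0.0564] = Φ(0.85) = 0.80. The same formula gives 44% at 10 points, 51% at 11 and 88% at 18.

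**The case against.** The case against is substantial on framing.

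- **The niche sentence gives a direction.** It says incidence was higher in group I. The flat statement of no significant difference is made about complaints, and there too it follows a sentence saying complaints were more common in group I. A reader might infer that the SAP declares the two techniques equivalent for niche; it does not. The protocol leaves interpretation to a Discussion that is not among the documents.
- **The arm percentages are printed.** Subtraction gives the point difference: 28.0 - 20.8 = 7.2 and 10.4 - 6.4 = 4.0. This is right, but subtraction gives no measure of precision, and that is the important omission.
- **Power must not be overstated.** A reader might infer from the upper limit near 18 points that the trial would usually miss an excess that large. It would not: power at 18 points is 88%. A non-significant result is the more likely outcome only for true differences below about 11 points. Nor would power calculated at the observed difference help, since it largely restates the P value.
- **An effect measure chosen now is post hoc.** Neither document planned one and the results are already tabulated. This stands, and the additions should be labelled accordingly.

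These points narrow the concern to missing intervals and conclusions worded from a threshold. They do not remove it.

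**Conclusion.** The point holds in this form. Both comparisons are inconclusive, and the reporting does not let a reader see it. The niche data are compatible with anything from about 3 points fewer to about 18 points more niches with dissection, and the complaint data with 3.1 points fewer to 11.3 points more. How the missing woman is counted moves the niche limits by less than one point and does not change this reading.

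A reader might equally take the direction of both results as showing harm from dissection. The documents do not support that, since both intervals include zero.

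The figures assume 125 randomised per arm, that Table 4 lacks only one woman, and that the remaining counts in Tables 4 and 6 are correct. The detectable difference of about 16 points also assumes a 20.8% base, which is the observed group II rate and not a planning value. The weakness lies in presentation and interpretation; the data themselves can still be used.

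**What to change.** 1. Account for the missing group I woman in Table 4 and state the denominator used.
2. Add the risk difference with its Newcombe 95% CI, and the risk ratio, to Table 4 and to the Yes/No comparison in Table 6. Label them as added after the results were tabulated.
3. Recompute the P values as two-sided and say so. For niche, the Pearson P is 0.14 to 0.19 depending on the denominator. For complaints, print one P for the two-by-two table (0.254) in place of 0.621 and 0.102.
4. Word both conclusions from the intervals as inconclusive, giving the limits.
5. State that 125 per arm gives 80% power only for a difference of about 16 points from a 20.8% base. Do not report power at the observed difference.

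The cost is a little more analysis, two columns in each of two tables, reworded sentences, and a less definite conclusion. No new data or patients are needed.
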